Original protocol	24 AUG 2020	Master Protocol Protocol Part A Protocol Part B

Amendment 4 (09 FEB 2023)

This amendment is considered to be substantial based on the criteria set forth in Article 10(a) of Directive 2001/20/EC of the European Parliament and the Council of the European Union.

Overall rationale for Amendment 4:

A description of changes and a brief rationale is outlined in the table at the end of this section. An overview is given below.

Clarification of dose-titration instructions

Clear blood pressure limits were added to the titration instructions to provide more precise guidance on when to maintain and not increase the dose. This amendment is expected to improve participant's safety and to result in more consistent titration decisions across sites.

In addition, two dose reductions are now permissible instead of a single dose reduction.

This change is considered substantial as it has effects on participant's safety.

Primary endpoint after 48 weeks instead of after 24 weeks of treatment

2-step DRSS improvement is the main efficacy endpoint in this clinical study. Assessments are planned after 12, 24, and 48 weeks of treatment. The assessment after 24 weeks was initially defined as the primary endpoint. However, information was received from other clinical trials in non-proliferative diabetic retinopathy, that achieving 2-step DRSS improvement in a sufficient number of study participants may take longer than 24 weeks for most drugs not administered by intravitreal injection (e.g. ROBIN trial NCT03238963, discussed in (Boyer et al. 2021). To provide sufficient time for the treatment effect, the primary assessment of this endpoint is moved to 48 weeks of treatment. Up to the date of this amendment, on-treatment DRSS assessments were not transferred from the central reading center into the study database, they were not seen by the sponsor nor by the independent data monitoring committee, in agreement with study procedures. No interim assessment was performed until now. Thus, no efficacy data from the present study were reviewed and the decision for this amendment was solely driven by general considerations triggered by

09 FEB 2023 Page: 3 of 95

information received from other clinical trials in diabetic retinopathy. Based on these considerations, a power adjustment is not deemed necessary.

This change to the primary endpoint assessment is considered substantial.

A full overview of changes is provided in the two tables below.

09 FEB 2023 Page: 4 of 95

Key changes in study design and other substantial changes

Section # and Name	Description of Change	Brief Rationale
Section 1.1 Synopsis Section 1.2 Schema Section 3 Objectives and endpoints Section 4.1 Overall design Section 4.2 Scientific rationale for study design	The primary DRSS assessment was moved to 48 weeks of treatment.	Information was received from other clinical trials in non-proliferative diabetic retinopathy, that achieving 2-step DRSS improvement in a sufficient number of study participants may take longer than 24 weeks for most drugs not administered by intravitreal injection (e.g. ROBIN trial NCT03238963, discussed in (Boyer et al. 2021). To increase the probability of a successful clinical trial, the primary
Section 4.4 End-of-study definition Section 8 Study assessments and procedures		assessment of this endpoint is moved to 48 weeks of treatment
Section 9.1 Statistical hypotheses Section 9.4.2 Primary endpoint		
Section 9.4.3.1 Efficacy Section 2.3.1 Risk assessment	Safety information from CONCORD study was updated.	Update of new information included in the IB
Section 6.5.1 Intra-individual dose-titration decisions	Minimum treatment interruption in case of pertinent adverse event extended to 48 hours.	Correction and extension of minimum temporary discontinuation interval
Section 4.1.2 Part 2 – Proof of concept Section 8.4 Pharmocokinetics Section 9.5 Interim analysis	No interim analysis is planned. DMC oversight will continue as planned.	With the primary endpoint moved to the end of the treatment period, the interim assessment is no longer deemed useful.
Section 6.5.1 Intra-individual dose-titration decisions Section 7.1.3 Re-challenge / re-start of study intervention	The dose-titrations instruction was specified by providing minimum blood pressure requirements for dose titration.	This amendment is expected to improve participant's safety and to result in more consistent titration decisions across sites. (substantial amendment)
Section 6.5.1 Intra-individual dose-titration decisions	Up to two (instead of only one) dose reductions are permissible	Allowing only a single dose reduction and imposing permanent treatment discontinuation in case a single dose reduction does not sufficiently improve tolerability may result in undue early treatment discontinuations and reduce the power of the clinical trial
Section 7.1.1 Permanent discontinuation	If study intervention is permanently discontinued, an End-of-Treatment visit should be performed in line with Visit 15. The participant remains in the study for continued assessment of study outcomes following the visit schedule in section 1.3.	Clarification of the visit schedule for study intervention permanent discontinuation

09 FEB 2023 Page: 5 of 95

Section # and Name	Description of Change	Brief Rationale
Section 7.1.1 Permanent discontinuation	Withdrawal from trial is no longer mandatory, in case of vision threatening complication or progression to PDR, but to be decided case by case by the investigator.	There is no safety concern with continuing treatment after a vision threatening complication. Continued treatment may be beneficial. Therefore, treatment discontinuation is not mandatory in general but to be considered case by case by the investigator.

Clarifications and corrections (non-substantial)

Section # and Name	Description of Change	Brief Rationale
Section 1.3 Schedule of activities (SoA)	Footnotes were added to clarify the timepoints for safety, blood sampling and ophthalmology examinations.	Clarification of sequence of activities
Section 1.3 Schedule of activities (SoA)	Administer study intervention (after blood draws) was removed at Visit 15 EoT. Dispensation of urine pregnancy test was added at Visit 12. 7-field color fundus photography (DRSS) was removed at Visit 8.	Corrections of mistakes: Assessing DRSS assessment after 8 weeks of treatment in addition to after 12 weeks of treatment cannot be expected to provide relevant additional data.
Section 7.1.2 Temporary discontinuation	If the re-assessed laboratory result indicates a decrease in eGFR <40% from baseline, study intervention may be re-started at the same dose as before this temporary discontinuation, in line with section 7.1.3.	Clarification on re-starting study intervention

09 FEB 2023 Page: 6 of 95

Table of contents

Tit	le page	1
Pro	otocol amendment summary of changes table	2
Tal	ble of contents	6
Tal	ble of tables	8
	ble of figures	
1.	Protocol summary	
1.1	Synopsis	
1.2		
1.3	Schedule of activities (SoA)	
2.	Introduction	16
2.1	Study rationale	
2.2	Background	18
	2.2.1 Disease background	18
	2.2.2 The role of soluble guanylyl cyclase in diabetic retinopathy	18

09 FEB 2023 Page: 10 of 95

1. Protocol summary

1.1 Synopsis

Protocol title:

A Phase 2 randomized, placebo-controlled, double-masked proof-of-concept study to investigate the efficacy and safety of runcaciguat (BAY 1101042) in patients with moderately severe to severe non-proliferative diabetic retinopathy

Brief title: Non-proliferative diabetic retinopathy treated with runcaciguat

Overall study plan:

Study 20739 is a Phase 2 proof-of-concept study that includes a subpart with PK/PD assessments (Part 1). Part 1 enrolls a subset of patients at a more intense investigation in specific study sites. Part 2 is the main PoC part, to be conducted in ophthalmology sites, that enrolls the majority of participants. PoC will be based on the evaluation of outcomes in participants from both parts.

Rationale:

Results from previous Phase 1 studies in healthy as well as renally impaired patients as well as a phase 2 study with patients with chronic kidney disease have demonstrated that runcaciguat given as modified-release oral tablets was well tolerated and support the start of further studies in patients.

Due to the mode of action of sGC activators, and based on preclinical data, it is assumed that sGC activators, administered to NPDR patients, can positively influence retinal perfusion and thereby improve fundus morphology and reduce the progression of retinal ischemia and vision-threatening later stages like PDR and/or DME.

The present study is to be conducted to obtain information on sGC activators by investigating

- 1. whether runcaciguat improves the diabetic retinopathy score in patients with moderately severe to severe NPDR
 - and to
- 2. explore the pharmacokinetic pharmacodynamic relationship of runcaciguat on retinal perfusion

The results are intended to provide useful information to improve the design of clinical studies with subsequent sGC activators, for example by supporting the choice of the appropriate dose and treatment duration.

09 FEB 2023 Page: 11 of 95

Objectives and endpoints:

Table 1-1 Study objectives and endpoints

Objectives	Endpoints
Primary objective: Efficacy Establish the proof-of-concept for the efficacy of the sGC activator runcaciguat	 Primary endpoint: DRSS improvement ≥ 2 steps at 48 weeks of treatment in the study eye
in the treatment of NPDR.	 Secondary endpoints for primary objective: Vision threatening complications at 48 weeks of treatment in the study eye DRSS improvement ≥ 2 steps at 24 weeks of treatment in the study eye
	 Other endpoints (for primary objective): Change in visual acuity from baseline Change in leakage area on Fluorescein Angiography DRSS changes from baseline in the study and fellow eye Vision threatening complications in any eye up to 48 weeks of treatment
Secondary objective: Safety Investigate the safety and tolerability of runcaciguat in patients with NPDR	Secondary endpoints for secondary objective: • Frequency of treatment-emergent adverse events • Other endpoints (for secondary objective): • Laboratory parameters • Vital signs • Electrocardiography
Other objectives Characterize pharmacodynamic effects of runcaciguat in patients with NPDR	Other endpoints
Characterize pharmacokinetics of runcaciguat in patients with NPDR	 Population pharmacokinetics Pre-dose (trough) plasma concentrations of runcaciguat by visit

DRSS = Diabetic Retinopathy Severity Scale; NPDR = Non-proliferative diabetic retinopathy;

Overall design:

This is a randomized, double-masked parallel study with two study arms enrolling N=98 patients with non-proliferative diabetic retinopathy. The study is conducted as a placebo-controlled study, for details see Section 6.3.

Total treatment duration is 48 weeks. The primary endpoint will be the number of participants with $a \ge 2$ -step improvement (reduction) in the DRSS after 48 weeks of treatment in the study eye.

A steering committee consisting of ophthalmologists and diabetologists (masked) is put in place to provide scientific and operational recommendations to the study protocol and may be consulted to support decisions in study conduct. An independent Data Monitoring Committee is set up to provide recommendations based on unmasked review of data, if needed.

Brief summary:

This Phase 2 study is conducted to determine whether runcaciguat, administered at once daily oral doses of a modified-release formulation, is more effective in treating NPDR than placebo.

09 FEB 2023 Page: 12 of 95

The study comprises two subparts, 1 (PK/PD) and 2 (proof of concept); both subparts will be conducted in parallel.

To assess the efficacy, the retinal morphology will be investigated by 7-field color fundus photography (CFP) supported by 7 Field FA images for the assessment of the DRSS by a central reading center. Two-step DRSS improvement at 48 weeks of treatment will be the primary efficacy endpoint. Additional DRSS assessments are done after 12 and 24 weeks of treatment. In addition, vision-threatening complications will be recorded throughout the study and assessed as secondary efficacy endpoint.

During the course of the study, 16 visits are planned, including the screening visit (Visit 1) and the end-of-study visit (Visit 16). Visit intervals are weekly during the first 4 weeks, while the dose of runcaciguat (or placebo) is titrated to the target dose, then fortnightly for the next 4 weeks and then every 4 weeks up to Week 25 (Visit 12). The subsequent visits, up to end of treatment in Week 49 (Visit 15), will be at 8-week intervals. The end-of-study visit, Visit 16, will take place 4 weeks later.

Number of participants:

A combined total of approximately 98 participants for Part 1 and 2 will be randomly assigned for an estimated total of \geq 40 participants per intervention group evaluable for primary endpoint assessment, as defined in Section 9.2. The estimated screen failure rate is approximately 50%.

Intervention groups and duration:

Participants are randomly assigned to one of two study arms. Assignment will be masked, as detailed in Section 6.3. After providing informed consent, participants will be screened (Visit 1) and within up to 4 weeks, eligible participants will be randomized and treatment will be initiated at Visit 2. During the initial four weeks, treatment will be titrated to the target dose of 120 mg runcaciguat or matching placebo. Treatment will start at 30 mg runcaciguat or placebo once daily for the first week. If well tolerated, the dose will be increased to 60 mg runcaciguat or placebo at Visit 3 in the second week of treatment, then to 90 mg runcaciguat or placebo at Visit 4 in the third week of treatment, and finally to 120 mg runcaciguat or placebo at Visit 5.

In case of intolerability (see Section 6.5.1) treatment may continue without up-titration or the dose may be reduced by one titration step.

Treatment will continue at the highest tolerated dose until completion of 48 weeks of treatment if tolerated, or until development of a vision threatening complication or development of PDR.

[figure not shown]
An end-of-study visit will be performed 4 weeks after end of treatment. This includes both participants who complete the planned treatment period, and participants who discontinue treatment early including treatment discontinuation due to vision threatening complications.

Data monitoring / Other committee: Yes

09 FEB 2023 Page: 13 of 95

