7.1 Discontinuation of study intervention

7.1.1 Permanent discontinuation

In rare instances, it may be necessary for a participant to permanently discontinue (definitive discontinuation) study intervention. If study intervention is permanently discontinued, an End-of-Treatment visit should be performed in line with Visit 15. The participant remains in the study for continued assessment of study outcomes following the visit schedule in section 1.3.

Unscheduled visits may be performed as deemed appropriate by the investigator, in particular in case of withdrawal because of an adverse event.

Participants *must* be withdrawn from the *study intervention* for any of the following reasons:

- Increases in transaminases as described in Table 10-3 (confirmed by analysis of two blood samples; additional laboratory examinations may be performed if necessary):
- Safety concerns for a participant by the investigator or the sponsor, e.g. due to obvious non-compliance.
- Pregnancy (see Section 8.3.5 for details)
- Temporary discontinuation exceeding 14 consecutive days or 21 days overall

Participants *may* be withdrawn from the *study intervention* for any of the following reasons:

- Repeated incidents of relevant hypotension or tachycardia
- Repeated temporary discontinuation of study intervention
- Vision threatening complication or progression to PDR

Necessity to withdraw the participant from the study will be assessed case by case by the investigator.

09 FEB 2023 Page: 45 of 95

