Repeat or unscheduled samples may be taken for safety reasons or for technical issues with the samples.

After signing an informed consent, participants will be invited to a screening visit, Visit 1, to evaluate their eligibility for this study. Eligible patients with NPDR who meet all of the inclusion criteria and none of the exclusion criteria, will be randomized to treatment with either runcaciguat or placebo. During the treatment period, participants will be monitored for adverse events and concomitant medication, and undergo the assessments outlined in the SoA, Section 1.3.

The treatment period comprises Visits 2 to 15 (Week 1 to Week 49), the End-of-Treatment visit.

An End-of-Study visit, Visit 16, is planned approximately 28 days after last administration of study drug.

- The maximum amount of blood collected from each participant over the duration of the study, including any extra assessments that may be required, will not exceed 300 mL.
- Repeat or unscheduled samples may be taken for safety reasons or for technical issues with the samples.

09 FEB 2023 Page: 48 of 95

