8.1.2 Vision-threatening complications

Vision-threatening complications are defined as occurrence of any of the following adverse events:

- PDR
- Any ocular neo-vascularization

09 FEB 2023 Page: 51 of 95

- Center-involved (ci) (central ETDRS subfield) DME
- Drop of BCVA of 10 letters or more from baseline

The assessment will be continued after treatment discontinuation if possible.

Treatment of the vision threatening complication should follow local standards and guidelines, i.e. treatment of ci DME with anti-VEGF or other appropriate measures, at the discretion of the investigator.

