Participants are randomly assigned to one of two study arms. Randomization will be done stratified by baseline DRSS (47 or 53). A combined total of approximately 98 participants for Part 1 and 2 will be randomly assigned for an estimated total of  $\geq$  40 participants per intervention group evaluable for primary endpoint assessment.

During the initial 4 weeks, treatment will be titrated to the target dose of 120 mg runcaciguat or matching placebo. Treatment will continue at the highest tolerated dose until completion of 48 weeks of treatment if tolerated, or until development of a VTC or development of PDR.

An EoS visit will be performed 4 weeks after EoT. This includes both participants who complete the planned treatment period, and participants who discontinue treatment early including treatment discontinuation due to VTC.

The study population is characterized by the following main inclusion criteria:

- Age  $\geq 18$  years
- Moderately severe to severe NPDR in the study eye: DRSS levels 47 or 53
- Diabetes type 1 or 2

- BCVA ETDRS letter score in the study eye of  $\geq$  69 letters (approximate Snellen equivalent of 20/40 or better)
- Refraction with a spherical equivalent from -6 dpt to +5 dpt

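### The protocol synopsis and SAP 1.2 still end the study 4 weeks after an early treatment stop, and still stop treatment at a VTC or PDR, against Protocol 7.1.1 as amended (minor, wording)

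*Protocol*

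**What the plan says.** **End of study after an early stop.** The synopsis (Protocol 1.1, intervention groups and duration) says "An end-of-study visit will be performed 4 weeks after end of treatment" and extends this to "participants who discontinue treatment early including treatment discontinuation due to vision threatening complications". SAP 1.2 has the same rule: "An EoS visit will be performed 4 weeks after EoT. This includes both participants who complete the planned treatment period", and then adds those who stop early. The synopsis numbers the end-of-study visit as Visit 16. Protocol 7.1.1 asks for an end-of-treatment visit modelled on Visit 15 when treatment stops for good, and then says "The participant remains in the study for continued assessment of study outcomes following the visit schedule in section 1.3". That schedule puts Visit 15 on day 337 and Visit 16 on day 365.

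**Stopping at a VTC or PDR.** The synopsis and SAP 1.2 describe treatment as running to 48 weeks unless a VTC or PDR develops first. Protocol 7.1.1 lists these only among the reasons for which a participant may be taken off treatment, at the investigator's judgement.

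**What shows intent.** The Amendment 4 summary explains the 7.1.1 visit text as "Clarification of the visit schedule for study intervention permanent discontinuation" and, for the second item, says "Withdrawal from trial is no longer mandatory, in case of vision threatening complication or progression to PDR". On VTCs, Protocol 8.1.2 says "The assessment will be continued after treatment discontinuation if possible". SAP 4.1.4 invites treatment stoppers to all protocol visits, but lists their later values without putting them into summary statistics.

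**The concern.** A participant who stops at Week 10 cannot both have the end-of-study visit around day 99 and stay on a schedule that ends on day 365. Nor can treatment both end at a VTC and be left to case-by-case judgement. A site or data manager working from the synopsis would release early stoppers about 4 weeks after the stop, and those visits cannot be recovered.

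Two analyses use the visits at stake:

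- **VTC in the study eye (secondary).** SAP 4.3.1.2 uses Kaplan-Meier and censors a study dropout without a VTC at the last visit. Protocol 9.4.3.1 words it as the last visit with evidence of no event. A stopper released at 4 weeks leaves the risk set then.
- **Multiple-imputation sensitivity analysis.** SAP 4.2.3 imputes response where the Week-48 DRSS is missing because of early discontinuation. Under the stale text that value is always missing for a stopper; under 7.1.1 it may exist.

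**Working it through.** **1. The plan's own figure.** Exact enumeration with 40 evaluable per arm, response 10% against 35%, Beta(0.5, 0.5) priors and both posterior criteria gives a proof-of-concept probability of 0.903 (0.889 with 39 per arm). This reproduces the stated figure of at least 90%. The visit rule does not enter that calculation.

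**2. Follow-up lost per stopper under the stale text.** For a stop after s weeks, 48 − s weeks remain and 48 − (s + 4) = 44 − s are lost. The stop day is 1 + 7s and the end-of-study day is 28 later. Visit days come from Protocol Table 1-4: V9 85, V10 113, V11 141, V12 169, V13 225, V14 281, V15 337.

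| Stop | Stop day / end-of-study day | Weeks lost | Visits lost up to V15 |
|---|---|---|---|
| Week 10 | 71 / 99 | 34 of 38 | V10–V15 (6) |
| Week 26 | 183 / 211 | 18 of 22 | V13–V15 (3) |
| Week 40 | 281 / 309 | 4 of 8 | V15 (1) |

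For the Week-10 stop, the lost visits hold 5 BCVA tests (V10, V12–V15), 6 OCTs and the Week-24 and Week-48 DRSS. Visit 9 falls inside the 4-week window and is not counted as lost. All three stops lose the Week-48 DRSS.

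**3. Illustrative effect on a Kaplan-Meier estimate, one arm.** The documents give neither the VTC risk nor the stopping rate, so these inputs are assumptions: 48-week risk R, a fraction f of those event-free stopping at Week 10, and a later hazard ratio HR in stoppers. Let h = −ln(1 − R)/48.

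- Full follow-up: 1 − e^(−10h) × [(1 − f)e^(−38h) + f e^(−38·HR·h)]
- Stoppers censored at Week 14: 1 − e^(−10h) × [(1 − f)e^(−4h) + f e^(−4·HR·h)] × e^(−34h)

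| R, f | HR 2: full / censored | HR 0.5: full / censored |
|---|---|---|
| 10%, 5% | 10.36 / 10.04 | 9.81 / 9.98 |
| 20%, 10% | 21.30 / 20.15 | 19.26 / 19.93 |
| 30%, 15% | 32.58 / 30.31 | 28.41 / 29.84 |

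With HR 1 the two agree. Doubling the hazard understates risk by 0.3 to 2.3 points; halving it overstates risk by 0.2 to 1.4 points.

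**4. Scale against sampling error.** With 46 to 52 randomized per arm, the binomial standard error is √(0.10 × 0.90/52) = 4.2 points at the low end and √(0.30 × 0.70/46) = 6.8 points at the high end. Every bias above is smaller.

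**5. A condition on step 3.** The difference exists only if post-stop VTCs are counted. If the SAP 4.1.4 exclusion of post-stop values were applied to the Kaplan-Meier analysis, the two visit rules would give the same estimate.

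**The case against.** The strongest reply is that the documents already answer the question. Protocol 7.1.1 is the operative section on permanent discontinuation, and Amendment 4 put the sentence there to clarify the schedule. Protocol 8.1.2 continues VTC assessment. Section 8.3.1 collects adverse events to 28 days after treatment or to the follow-up visit, whichever is later. SAP 4.1.4 invites stoppers to every visit. SAP 1.2 is a design recap and does not schedule visits. Censoring applies to those who leave the study, so a stopper who still attends is not censored. All of this stands, and it is why the point is minor. It does not remove the conflict: the synopsis and SAP 1.2 name early stoppers expressly, so they cannot be read as describing completers only.

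The effect may also be smaller than illustrated. The main VTC analysis is on the per-protocol set. If planned intake means 48 weeks, a Week-10 stopper has 10/48 = 21% compliance and is excluded, so only the FAS sensitivity analysis would be touched. That depends on how planned intake is counted and on a separate validity document that is not available. No between-arm bias is shown, and similar stopping in both arms would at least partly cancel.

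A reader might infer more from the conflict, but the documents do not support it:

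- **That the primary result, sample size or proof-of-concept rule is at risk.** SAP 4.2.2 uses a while-on-treatment rule with last observation carried forward for later dropouts, and non-response for dropout before Visit 9. SAP 4.1.4 uses dropout to mean leaving the study, so someone off treatment but still attending is not perfectly assigned. Even so, both the strategy and the exclusion of post-stop values point away from using an off-treatment Week-48 value.
- **That sites are releasing stoppers early.** No document shows which text sites follow.
- **That Section 8 is a third contradiction.** It says "An End-of-Study visit, Visit 16, is planned approximately 28 days after last administration of study drug" without mentioning early stoppers, so it describes the ordinary course.

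Whether an off-treatment Week-48 DRSS enters the multiple imputation is a separate gap. It arises under 7.1.1 itself and would remain after the synopsis is corrected.

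**Conclusion.** The concern holds as a minor error in current text. On two matters, the timing of end of study and stopping at a VTC or PDR, the synopsis and SAP 1.2 state rules that contradict Protocol 7.1.1 as amended.

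Confidence is high for the contradiction and for the follow-up lost per stopper. It is low for any numerical bias, because R, f and HR are assumed, every stopper is placed at Week 10, and the number affected is unknown; 7.1.1 expects permanent stops to be rare. The exposed results are the secondary VTC analysis, and only if stoppers' later hazard differs and their events count, and possibly one sensitivity analysis.

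**What to change.** 1. In the protocol synopsis and SAP 1.2, state that participants who stop treatment early have an end-of-treatment visit in line with Visit 15 and a 28-day safety follow-up that is not end of study, and then continue the remaining scheduled visits through Visits 15 and 16.
2. In the same two places, replace the statement that treatment runs until a VTC or PDR with the case-by-case rule of 7.1.1.
3. In SAP 4.3.1.2, state that VTCs observed after treatment stop count in the Kaplan-Meier analysis, consistent with Protocol 8.1.2, and that the SAP 4.1.4 exclusion of post-stop values does not apply to it.

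The cost is wording in the synopsis and two SAP sections, with no visits beyond those 7.1.1 already requires. The third change is worth making before unmasking even if all visits are complete, because it removes a choice that would otherwise be made with the data in view.
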